8.12.3 Local Skin Reactions

The frequency of the individual LSRs (Investigator assessed: erythema, edema, erosion/ulceration, scaling/dryness, and scabbing/crusting; Subject reported: itching and pain) will be tabulated by severity and treatment group at each visit. In addition, the change from Screening at Visit 5/EOT will be dichotomized to no change/improved versus worsened and will be tabulated by treatment group. The frequency of the individual LSRs recorded by subjects in weekly diaries (redness, swelling, erosion/ulceration, scaling/dryness, and scabbing/crusting, itching, and pain) will be tabulated by severity and treatment group for each study week.

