5.3. Application of Study Drug

Administerers of study drug should wash their hands and wear non-powdered nitrile gloves for application.

At clinic: Subjects will wash their face with Cetaphil® right before in-office application on Day 1. Subject's dose will be administered by the PI (or sub-investigator designee) at the Day 1 visit after swab samples have been procured.

At home: From Day 2 and thereafter, subjects will apply study drug every evening after their Cetaphil® wash. Subjects will be instructed to stop study drug application 3-7 days before Visit 5.

Used study drug pads, shrink-wrap packaging (bags) and application gloves will be discarded in a standard waste receptacle at either the clinical site or at the subject's home. Once the study drug has been applied, the administerer will dispose of the used pad and bag by pinching the pad and bag together with the gloved hand and, using the ungloved hand, peel off the glove inside-out thereby containing the pad and bag within the glove. The subject will discard the glove (with pad and bag contained inside) in a standard waste receptacle and wash hands thoroughly with soap and water.

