- f** Blood pressure, heart rate, temperature.
- g** CBC is assessed locally and must include Differential.
- h** Urine dipstick test assessed locally.

- i** All screening visit procedures will be completed prior to initiating BPO pre-treatment. BPO gel should be applied for at least 5 days, in the AM immediately after the AM Cetaphil® wash. Final BPO pre-treatment should be approximately 24 hours prior to application of study drug.
- j** Study subjects will note date and time of each BPO pre-treatment and Cetaphil® wash for the Screening period, and date and time for each Cetaphil® wash and study drug application during the study treatment period.
- k** Subjects must not wash, shave, apply make-up or other products to their face, and subjects must hold their application of study drug, on clinic visit days.
- l** Subjects will wash their face with Cetaphil® cleanser twice daily beginning at the Screening visit throughout the Week 12/EOT visit. No other face wash products may be used during the Subject's participation in the study.
- m** Subjects will wash with Cetaphil® at the clinic after all other Day 1 procedures have been completed and immediately prior to study drug application by the PI.
- n** Screening samples are obtained prior to initiation of BPO pre-treatment.
- o** Follicular engraftment sampling is completed via use of Biore® Strips applied across the bridge of the nose extending to either cheek.
- p** The Week 12/EOT visit will take place between 3 to 7 days following the Subject's final study drug application. The PI should inquire regarding the subjects understanding of and compliance with study drug application procedures and re-instruct, as necessary.
- q** Week 12/EOT follicular engraftment sampling will be obtained after facial washing via Biore® strip at the clinic and should be completed 3 to 7 days following the last study drug application.
- r** Study drug is applied by the PI (or sub-I designee) on Day 1; study drug is applied by the Subject daily thereafter in the evenings.
- s** Study procedures are completed as is clinically indicated for vital signs, physical exam, urine pregnancy, and CBC for unscheduled study visits.
- t** EOT procedures should be completed at the Week 12 visit. Should the subject discontinue the study prior to Week 12 (Visit 5), the EOT procedures should be scheduled and completed as soon as possible.
- u** Dispense Subject Diary to the subject.

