3.4 Primary Safety Endpoints

The safety endpoints are:

- Incidence (severity and causality) of any local and systemic AEs
- Proportion of subjects with presence (and severity) of each LSR at each time point
- Changes from Screening/Baseline to EOT in physical examination findings
- Changes from Screening/Baseline to EOT in vital signs
- Changes from Screening to EOT in CBC results

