- b** Day 1 procedures must be completed prior to the application of study drug. Day 1 study drug is applied by the PI or sub-investigator designee at the site.
- c** Limited physical examination of face, chest, arms, back (relevant acne regions).
- d** Adverse Events are assessed from the time of consent.
- e** Subjects will remain at the clinic for at least 30 minutes after the initial (Day 1) study drug application to be assessed for AEs.
- f** Blood pressure, heart rate, temperature.
- g** CBC is assessed locally and must include Differential.
- h** Urine dipstick test assessed locally.
- i** All screening visit procedures will be completed prior to initiating BPO pre-treatment. BPO gel should be applied for at least 5 days, in the AM immediately after the AM Cetaphil® wash. Final BPO pre-treatment should be approximately 24 hours prior to application of study drug.
- j** Study subjects will note date and time of each BPO pre-treatment and Cetaphil® wash for the Screening period, and date and time for each Cetaphil® wash and study drug application during the study treatment period.
- k** Subjects must not wash, shave, apply make-up or other products to their face, and subjects must hold their application of study drug, on clinic visit days.
- l** Subjects will wash their face with Cetaphil® cleanser twice daily beginning at the Screening visit throughout the Week 12/EOT visit. No other face wash products may be used during the Subject's participation in the study.
- m** Subjects will wash with Cetaphil® at the clinic after all other Day 1 procedures have been completed and immediately prior to study drug application by the PI.
- n** Screening samples are obtained prior to initiation of BPO pre-treatment.
- o** Follicular engraftment sampling is completed via use of Biore® Strips applied across the bridge of the nose extending to either cheek.
- p** The Week 12/EOT visit will take place between 3 to 7 days following the Subject's final study drug application. The PI should inquire regarding the subjects understanding of and compliance with study drug application procedures and re-instruct, as necessary.
- q** Week 12/EOT follicular engraftment sampling will be obtained after facial washing via Biore® strip at the clinic and should be completed 3 to 7 days following the last study drug application.
- r** Study drug is applied by the PI (or sub-I designee) on Day 1; study drug is applied by the Subject daily thereafter in the evenings.

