7.2 Local Skin Reactions

Local skin reactions (LSRs) will be assessed at each visit using a four-point ordinal scale: 0-absent, 1-mild (slight, barely perceptible), 2-moderate (distinct presence) and 3-severe (marked, intense). The investigator will assess erythema, edema, erosion/ulceration, scaling/dryness, and scabbing/crusting in the treatment area. Subjects will assess itching and pain in the treatment area. LSRs that require medical intervention, withholding or discontinuation of study drug application, or extend 2 cm beyond the treatment area will be documented as AEs.

In addition to the clinic visit assessments, subjects will maintain a daily diary to assess each of the seven LSR parameters. The subjects are to record the greatest severity of each LSR experienced during the previous 7 days (weekly score for Weeks 1 through 16).

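### The only within-subject worsening summary for local skin reactions is taken off drug at Visit 5, and no planned table counts subjects by worst on-treatment score

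*SAP*

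**What the plan says.** SAP 3.4 defines the LSR endpoint as "Proportion of subjects with presence (and severity) of each LSR at each time point". SAP 8.12.3 plans three descriptive outputs on the Safety population:

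- Clinic scores: the individual LSRs "will be tabulated by severity and treatment group at each visit".
- As an addition to that table, "the change from Screening at Visit 5/EOT will be dichotomized to no change/improved versus worsened".
- Diary scores: the individual LSRs "will be tabulated by severity and treatment group for each study week". Under SAP 7.2 each weekly entry is the worst grade of the preceding seven days, for Weeks 1 to 16.

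On timing, Protocol 5.3 states: "Subjects will be instructed to stop study drug application 3-7 days before Visit 5". The schedule footnotes in SAP 4 agree: "The Week 12/EOT visit will take place between 3 to 7 days following the Subject's final study drug application". On the reference value, Protocol Appendix 2, footnote i, states: "All screening visit procedures will be completed prior to initiating BPO pre-treatment". Screening scores therefore precede benzoyl peroxide (BPO).

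SAP 8.7.6 tabulates both Screening and Day 1 LSR severity by arm, but no change from Day 1 is planned. SAP 7.2 turns an LSR into an adverse event (AE) only if it needs medical intervention, leads to drug being withheld or stopped, or spreads 2 cm beyond the treatment area. SAP 8.12.2 summarises treatment-emergent AEs by unique subjects and maximum severity.

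**The concern.** For a product applied to the face every day, two tolerability questions matter most: how many subjects in each arm got worse on drug, and how bad it became at its worst. The plan's one table about a subject getting worse is taken after dosing has stopped. A reaction that arises in Week 3 and fades, or one that clears in the days after the last application, falls in its favourable category.

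The other tables do cover the dosing period, but as separate counts for each visit and week. A low weekly frequency could mean a few subjects with persistent reactions or many subjects with brief ones. These are different tolerability profiles, and the planned summaries would look the same for both. An LSR that meets none of the AE criteria, even one graded severe, does not reach the unique-subject, maximum-severity summary that AEs receive.

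**Working it through.** **1. The off-drug interval.** SAP 8.8 places the final dose on Study Days 73 to 77, and SAP Table 3 sets the Visit 5 target at Day 80. 80 − 77 = 3 and 80 − 73 = 7, which reproduces the stated 3 to 7 days. This is the schedule for completers. Under schedule footnote t, subjects who stop early have end-of-treatment procedures as soon as possible.

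**2. What the Visit 5 table records.** Two made-up subjects on the 0–3 scale:

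| Subject | Screening | Day 1 | Visit 3 | Visit 4 | Visit 5 | Change at Visit 5 | Scored |
|---|---|---|---|---|---|---|---|
| A | 0 | 0 | 0 | 2 | 0 | 0 | not worsened |
| B | 0 | 0 | 0 | 0 | 0 | 0 | not worsened |

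The dichotomy cannot tell A from B. The Visit 4 frequency table does count A's moderate score.

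**3. What the frequency tables can and cannot give.** Let k(w) be the number of subjects in an arm of size n with a moderate or severe score in week w. The number ever affected lies between the largest k(w), when the same subjects recur, and the smaller of n and the sum of the k(w), when they are different subjects each week. No independence assumption is needed.

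- Inputs: 36 randomised at 2:1 (Protocol 3.3), so n = 36 × 2/3 = 24 on NB01 if allocation is exact; 11 treatment weeks; k(w) = 1 in every week (assumed for illustration).
- Lower bound: 1/24 = 4%.
- Upper bound: 11 × 1 = 11, and 11/24 = 46%.

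All 11 weekly tables are identical at both ends of that range.

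**4. The Screening reference.** I enumerated all combinations of Screening, Day 1 and Visit 5 grades.

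- Day 1 grade at or above Screening (BPO raises the grade or leaves it unchanged): 20 combinations are worsened against Screening and 10 against Day 1. None is worsened against Day 1 only. Here the Screening reference can only add worsened calls.
- Day 1 grade below Screening: of 24 combinations, 10 are worsened against Day 1 only (for example 2, then 1, then 2).

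The documents do not say which direction to expect. Change from Screening therefore mixes BPO and study-drug effects, which is a question of attribution. The off-drug timing is what places resolved on-drug reactions in the not-worsened category.

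**The case against.** The strongest reply is that the Visit 5 dichotomy is a supplement. The endpoint is presence and severity at each time point, and the by-visit and weekly tables deliver that throughout dosing. Because each diary entry is the worst grade of the week, a reaction that is gone by Visit 5 still appears in the week it occurred. SAP 8.1 says tables will in general be supported by by-subject listings, and with 36 subjects worst grades could be counted by hand. LSRs that need intervention, affect dosing or spread already enter the AE summaries. No LSR test is planned, and SAP 8.3 allows further exploratory analyses.

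Most of this stands, and it limits the point to a missing summary. A reader might infer that the tolerability question as a whole is answered at a time point biased toward no effect. The documents do not support that, because on-drug severity is reported at Visits 3 and 4 and in every treatment week. A reader might also infer that the pre-BPO reference causes on-drug reactions to be scored as no change. Step 4 shows that it cannot if BPO raises grades or leaves them unchanged. Both arms also receive BPO, so the comparison between arms is not obviously biased by it.

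The reply does not remove the gap itself. Listings let a reader rebuild the count but do not report it by arm, and a table added after unblinding would have to be identified as unplanned.

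**Conclusion.** The point holds as a modest reporting gap in a primary safety endpoint. On-drug reactions are captured and the endpoint as worded is met. What is missing is any planned summary of how many subjects per arm ever worsened, or ever reached moderate or severe, while on drug. The one within-subject summary is taken 3 to 7 days after the last dose for subjects on schedule.

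The size is best shown by the bound: one affected NB01 subject per week is compatible with 4% to 46% ever affected. That rests on exact 2:1 allocation of 36 and an assumed count of one per week. How far the Visit 5 table would understate on-drug worsening cannot be estimated, because the documents give neither a reaction rate nor a resolution time.

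**What to change.** In SAP 8.12.3, for each LSR and arm:

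1. Add the number and percentage of subjects by worst on-treatment score, once from clinic Visits 3 and 4 and separately from diary Weeks 1 to 11. Keep the two apart because the raters and recall periods differ.
2. Apply the worsened / not-worsened dichotomy to clinic scores at Visits 3 and 4, against Day 1 pre-dose as well as Screening.
3. Keep the Visit 5 table, but label it as off-drug.

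This brings LSRs into line with the subject-level, maximum-severity summary that SAP 8.12.2 gives AEs. The cost is a few more descriptive tables. All the scores are already collected, and no assessment or visit changes.

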8.12.4 Physical Examination

Findings from the physical exam will be recorded in medical history (from assessment at Screening and Baseline) or as AEs (from assessment at Visit 5/EOT).

8.12.5 Vital Signs

Descriptive statistics of vital signs (temperature, blood pressure, and heart rate) will be provided by treatment group for Screening, Baseline and Visit 5/EOT, as well as, change from Screening at Visit 5/EOT.

8.12.6 Pregnancy Test

Results from UPTs will be provided in a listing.

8.12.7 Complete Blood Count

Local CBC tests will be evaluated for any material changes during the study period. All laboratory data will be listed and reported in the units received by the laboratory. Shift tables by analyte and by out of range flag will be presented.

8.12.8 Concomitant Medications and Concurrent Therapies/Procedures

Information on concomitant medications administered during the study and concurrent procedures performed during the study will be collected. Prior medications are medications with a stop date prior to the first dose of study treatment.

Concomitant medications will be summarized for the Safety population using the World Health Organization drug dictionary drug class (ATC3) and preferred name, overall, and by treatment group. All medication data will be listed.

Concurrent procedures will be listed.

Unknown start dates and end dates will be imputed based on the rules provided for AE.

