8.2 Analysis Populations

8.2.1 *Safety Population*

The Safety population will include all randomized subjects who received and applied study drug. Subjects will have their first application of test article applied in the clinic by the PI (or sub-I-designee) during their Baseline Visit on Day 1. Subjects will be included in a treatment group based on the treatment they received (even if not the treatment group to which they were randomized). If a subject administered more than one type of test article during the trial, then the subject will be included in the treatment group to which they were randomized.

8.2.2 *Modified Intent-to-Treat Population*

The modified intent-to-treat (mITT) population will include all randomized subjects who were dispensed the study drug and have at least one post-baseline assessment. Subjects will be included in the treatment group to which they were randomized, regardless of the treatment received.

8.2.3 *Per-Protocol Population*

The per-protocol (PP) population will include a subset of the mITT population who completed the study without significant protocol deviations (as will be determined prior to unblinding the randomization) and met the criteria as specified below. Subjects will be included in the treatment group based on the treatment received.

- Meets all inclusion criteria and does not meet exclusion criteria #1-11 and #13-22.
- Has not taken or applied any interfering concomitant medications/therapies.
- Completed Visit 5/EOT procedures on Days 71 to 90 with the visit occurring 1 to 10 days after the final application of test article.
- Applied at least 80% of the expected doses with no other evidence of material dosing non-compliance.

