8.12 Safety Evaluation

All safety analyses will be performed on the Safety population.

8.12.1 *Extent of Exposure*

The study drug is supplied as single-use cotton pads. The total amount of study drug used by each subject will be calculated based on the number of days the study drug was applied (according to the subject's diary entries).

8.12.2 *Adverse Events*

All AEs reported during the study will be listed, documenting course, severity, Common Terminology Criteria for Adverse Events (CTCAE) grade, PI assessment of the relationship to the study drug, and outcome. Verbatim terms on the eCRFs will be linked to preferred terms (PTs) and system organ class (SOC) using the Medical Dictionary for Regulatory Activities (MedDRA) mapping system. For all AE summaries, if a subject has more than one AE within a preferred term, the subject is counted once in that preferred term. If a subject has more than one AE within a system organ class, the subject is similarly counted once in that system organ class.

The number and percentage of unique subjects reporting each treatment-emergent AE will be summarized by SOC and preferred term. The number and percent of unique subjects reporting each treatment-emergent AE will also be summarized by SOC, preferred term, and maximum severity (mild, moderate, severe) and closest relationship to study drug (not related, unlikely, possibly, probably, definitely).

Dose limiting toxicities, if any, will be summarized by SOC, PT and treatment group.

Serious AEs, if any, will be summarized by SOC, PT and treatment group.

For any partial date, the general rules for imputation are:

- If only day is missing, then the 1st day of the month will be used.
- If only year is present, then 01Jan will be used.

If the imputed date is for an AE start date and is in the same year and month as the first dose date but before the first dose date, then the first dose date will be used, or if the imputed AE start date is after the AE end date, then the AE end date will be used. If the imputed date is for an AE start date and is in the same year and month as, but after the last dose date + 30 days, then the last dose date + 30 days will be used.

If the imputed date is for an AE end date and is after the death date, the date of death will be used, or if the imputed AE end date is before the AE start date, the AE start date will be used.

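### Partial end dates are imputed to the earliest possible day, so drugs still in use after first dose can be classed as prior; the same rule, and a first-dose floor limited to one month, can put some partly dated AEs before first dose

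*SAP*

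**What the plan says.** The imputation rules stand in SAP 8.12.2 (Adverse Events) and do not separate start dates from end dates: "For any partial date, the general rules for imputation are" followed by "If only day is missing, then the 1st day of the month will be used" and "If only year is present, then 01Jan will be used".

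The corrections that follow differ by type of date:

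- **AE start, first-dose floor.** If the imputed start "is in the same year and month as the first dose date but before the first dose date, then the first dose date will be" its replacement. A start imputed to another month is not covered.
- **AE start, later than the end.** "if the imputed AE start date is after the AE end date, then the AE end date will be used". There is no check against first dose.
- **AE end.** It is replaced by the death date if later than death, and by the start date if earlier than the start.

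No order is given between the two rules that repair a start later than an end.

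SAP 8.12.8 extends all of this to medications: "Unknown start dates and end dates will be imputed based on the rules provided for AE". It also defines the class that is kept apart from concomitant use: "Prior medications are medications with a stop date prior to the first dose of study treatment". SAP 8.2.3 requires of a per-protocol (PP) subject: "Has not taken or applied any interfering concomitant medications/therapies". The SAP summarises treatment-emergent AEs but does not define them. Protocol 7.2 ties the term to AE data collected from first dose to the final study visit.

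**The concern.** Taking the earliest possible day is a usual choice for a start date, because it tends to keep the record in scope. For an end date it works the other way: it shortens the interval and can close it before dosing began. Medication stop dates have no first-dose floor, so nothing corrects this.

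Stops close to first dose are to be expected. Protocol 5.4 records current drugs and those taken in the 30 days before Baseline, and Protocol 6.2.1 provides for washout of prohibited drugs in the screening period.

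At stake are the concomitant-medication summary, possibly the PP check on interfering medication, and, for AEs, whether an event with poorly known dates counts as treatment-emergent. AE incidence is a primary safety endpoint (SAP 3.4).

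**Working it through.** The plan gives no figure to reproduce and no count of partial dates. The check applies the stated rules to worked dates. First dose on 15 March 2019 is an assumption for illustration.

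**Medications (drug started before first dose)**

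- Stop recorded as March 2019, day missing: imputed to 01 March, before 15 March, so prior, even if the drug ran to 31 March.
- Stop recorded as 2019 only: imputed to 01 January, so prior, even if the drug was used throughout treatment.

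The size, given a day-missing stop in the month of first dose, follows from a grid of 30 possible first-dose days by 30 possible true stop days, all equally likely (an assumption):

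- all cells: 30 x 30 = 900
- truly in use on or after first dose: 30 x 31 / 2 = 465 (51.7%)
- of these, correctly kept, because first dose was on the 1st: 30
- called prior: 465 - 30 = 435, which is 435/465 = 93.5% of the truly concomitant and 435/900 = 48.3% of all cells

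On a 365-day calendar the corresponding shares of truly concomitant cases called prior are 5373/5738 = 93.6% (day missing, stop in the month of first dose) and 66430/66795 = 99.5% (year only, same year).

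**Adverse events**

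Three readings of the order are possible:

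- **A:** the start corrections run in sequence, then the end correction.
- **B:** the start corrections are alternatives, both tested on the imputed start, then the end correction.
- **C:** the first-dose floor, then the end correction, then the start-after-end rule.

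| Recorded start / end | Start under A | Start under B | Start under C |
|---|---|---|---|
| Mar 2019 / Mar 2019 | 01 Mar | 15 Mar | 15 Mar |
| Mar 2019 / 2019 | 01 Jan | 15 Mar | 15 Mar |
| Apr 2019 / 2019 | 01 Jan | 01 Jan | 01 Apr |
| 2019 / 2019 | 01 Jan | 01 Jan | 01 Jan |
| 2019 / 20 Apr 2019 | 01 Jan | 01 Jan | 01 Jan |

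The third row is an event known to have begun after first dose. It is moved before first dose unless the end date is repaired first. The last two rows do not depend on the order, nor on the end date being partial: 01 January is not in the month of first dose, so the floor does not apply.

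**The replacement rule on the same dates**

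With end dates set to the last day of the month or 31 December, both drugs above become concomitant. With the floor also extended to every compatible partial start, the AE starts in the first four rows become 15 March, 15 March, 01 April and 15 March. In the fifth row the complete end date of 20 April allows onset on treatment, so the start also becomes 15 March.

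On the 30 x 30 grid the last-day rule calls all 900 cells concomitant. It misclassifies the 30 x 29 / 2 = 435 cells in which the drug had truly stopped before first dose, and none of the 465 others.

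**The case against.** **The AE rules survive a plain reading.** The two start corrections are joined as alternatives. Read that way, March/March stays at first dose, because the imputed start and end are both 01 March and only the floor fires. This stands. A reader might infer that any AE with both days missing in the month of first dose is lost, but that needs the corrections to be run in sequence. The objection does not rescue April/2019 under the same reading, nor a year-only start under any.

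**Treatment-emergence may not depend on the imputed onset.** Protocol 7.2 defines it by when the data are collected, and pre-dose events mostly go to medical history. This also stands: the documents do not show that such AEs will leave the primary safety tables. But Protocol 6.2.1 keeps pre-dose SAEs and procedure-related AEs on the AE form, so presence on the form does not settle the matter, and the SAP states no derivation.

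**The PP effect is conjecture.** SAP 8.2.3 does not say that the interfering-medication check uses imputed dates. A reader might infer that PP membership is compromised; the text supports only a conditional risk.

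**The total error is the same either way.** The present rule and the last-day rule each misclassify 435 of 900 cells. That is correct, and the 93.5% should not be quoted without it. The case for change is the direction of the error, not its total.

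**The trigger is narrow and the result descriptive.** It needs a drug started before first dose and a partial stop in the month, or for year-only dates the year, of first dose. Ongoing drugs, and drugs known to have started on or after first dose, are unaffected. Medications are reviewed at each clinic visit, and all medications and AEs are listed. This stands and limits the weight of the point.

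**Conclusion.** The point holds on the text for medications: the stated rule classes the drugs described as prior for every first dose not on the 1st of the month (day missing) or not on 01 January (year only). The 93.5% is conditional on such a record existing and on uniform days.

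For AEs it holds as a possibility. A known post-dose month with a year-only end is moved before first dose under two of the three readings. A year-only start in the year of first dose is moved there under all three, unless first dose falls in January, where the floor applies. Whether that removes the event from a table depends on a derivation that the SAP does not state.

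The harm is to descriptive summaries and perhaps to PP membership; no listing loses a record. The number of affected records cannot be computed from the documents and is probably small. In an arm of about 24 (36 subjects, if split exactly 2:1), one affected subject would be 1/24 = 4.2%. The correction is cheap and worth making before unblinding.

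**What to change.** In SAP 8.12.2 and 8.12.8:

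1. Impute a partial end date to the last day of the month, or to 31Dec if only the year is known, capped at last contact or death.
2. Class a medication as prior only when the known parts of its stop date show that it ended before first dose.
3. Impute end dates before start dates, and state that order.
4. Set a partial AE start, year-only included, to first dose whenever the known parts of the start and end dates allow onset on or after first dose. Item 1 alone does not cure a year-only start.
5. State whether treatment-emergence and the PP medication check use imputed dates.

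The cost is a few sentences and a small programming change. The downside should be stated in the SAP: some drugs that had truly stopped before first dose will be counted as concomitant (435 of 900 cells on the grid above), and a pre-dose event on the AE form with a partial onset may be counted as treatment-emergent. Both errors are over-inclusive, which is the conservative direction for a safety summary.
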